#### 4.3 Statistical Methods

## 4.3.1 Data Handling

All data will be recorded either by the patient themselves or by the provider directly onto printed forms. The information will then be entered into spreadsheets using the assigned study identifier. Information will remain de-identified throughout the remainder of the study period and will remain on password protected, Mayo servers.

## 4.3.2 Power Analysis

This is the first study which will be performed for this specific device. As such, the objectives are to assess safety with various dosing protocols. Regarding our secondary end points of penile length and curvature improvement, prior studies evaluating the role of PTT in the early phase of PD have

demonstrated significant improvements with study sizes of 96 patients, which is consistent with the current study schema.[17]

A power analysis was also performed using ANOVA with anticipated sizing of 25 individuals into 4 arms. This provides an effect level of 0.3370 using 80% power, with 0.05 significance established for curvature assessment. Therefore, the study is likely powered to demonstrate large changes in curvature but may not be adequately powered to identify small or medium differences in curvature between groupings. The study is adequately powered to detect reasonable changes in penile length.

#### 4.3.3 Statistical Analysis

All data will be entered into JMP Pro 10.0.0 (SAS Institute, Cary, NC). Differences between groupings will be analyzed using tests appropriate to the specific conditions: Wilcoxon, matchedpairs, student's t-test, ANOVA, ANCOVA, chi-squared, or Fisher's tests. All relevant tests will be 2-sided, with a p-value of <0.05 defined as significant. Differences in AE's will be determined based on total number of reported events as well as individual assessments of each individual event.

During the first phase of the study, results will be analyzed as a whole to determine the percentage of men who were non-compliant (both in methods of utilizing the device and percentage of time spent using the device) or dropped out. These data will determine the ability of men to utilize the device as recommended. Data will be analyzed both with and without these non-compliant / dropout men included. Non-compliance will be determined by failure to bury the white indicator line regularly with straight stretch, failure to achieve 90 degree bending during majority of uses, and failure to perform traction for at least 90% of days recommended.

Analyses will be performed using comparisons within patients (changes from baseline to 3 months, from 3 months to 6 months, from baseline to 6 months) and between groupings. ANCOVA will be used (adjusting for baseline values of curvature direction, curvature degree, and baseline penile length). Additional analyses will be performed to analyze the impact of prior treatments (such as intralesional injections) on outcomes. The use of ANCOVA is anticipated to increase the effect size slightly to 0.302 (assuming R^2 value of 0.2 for curvature direction, curvature degree, and baseline penile length).

Assessments will also be performed comparing any degree of traction (i.e. groups 2-4) against no traction. Additional assessment will also be performed based on the total duration of traction applied (time per day multiplied by number of days used) to assess for differences in outcome variables.

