#### 2 SPECIFIC AIMS / HYPOTHESIS

## 2.1 Primary Objectives

1. Evaluate the safety of the RestoreX® device when used 30 minutes once daily, twice daily, three times daily, and in an open label fashion

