#### 4.1.5 Consent and Enrollment

Following initial recruitment, patients will be scheduled for an introductory and orientation appointment. Specific study details and requirements will be reviewed at that time, and if the patients express interest in participating, a formal consent will be reviewed.

If the patient successfully completes the consenting process, they will undergo initial assessments as described later in the protocol. At enrollment, all patients will be assigned a study identifier, with a master list maintained in a password protected database (Mayo server) linking the patient to the identifier. A goal of 25 patients will be enrolled into each arm of the study, with an estimated 120 enrolled to achieve this number (due to anticipated dropouts, failure to comply). It is estimated that 250 patients will need to be screened to enroll the 120 patients.

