## 4.2 Study Schema

Once patients have agreed to receive further information on the study, an initial consult will be established. Patients who are currently taking other therapies for PD will be requested to stop these therapies for a minimum of 4 weeks prior to the appointment to assure an adequate washout period prior to being enrolled.

During the initial appointment, the patient will receive a description of the study, initial education on how to use the device properly, and informed consent. Those consenting to the procedure will

receive initial study assessments (see below). Those wishing additional time to consider enrollment may be rescheduled to a later date if desired. Once consent is completed, the patients will be randomized into one of four groups: PTT 30 min 1x/day, 30 min 2x/day, 30 min 3x/day, or control (no treatment).

Patients will then begin using the devices as previously instructed for the times appropriate to their group. After 3 months (+1.5 months permitted), patients will return for subsequent assessments (see below). After completion of the subsequent assessments, patients will begin a 3-month, open-label phase of the trial. During this period, the patients will be allowed to use the device for 30 minutes at a time, with a frequency to be determined by the patient.

After completion of the open-phase portion of the trial, patients will undergo final assessments, which are identical to the 3-month assessments. Patients will then be encouraged to self-report any additional adverse events (AE's) that they encounter over the subsequent 3 months after discontinuing the therapy and will be contacted by telephone for a final question / adverse event assessment (9 months after study initiation).

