### 5.7.1 Sponsor-investigator Reporting: Notifying the Mayo IRB

An adverse event form will be completed for any serious adverse event. This will be reported to the Mayo IRB in a de-identified manner.

The study team will report to the Mayo IRB any UPIRTSOs and Non-UPIRTSOs according to the Mayo IRB Policy and Procedures.

Information collected on the adverse event form (and entered into the research database)

- Subject's ID
- Description of adverse event
- The date the adverse event occurred and resolved (if applicable)
- Intensity
- Outcome
- Action taken to address
- Relationship to study
- Impact on study withdrawal
- Classification as serious or not

The sponsor-investigator will review all adverse event reports to determine if specific reports need to be made to the IRB. The sponsor-investigator will sign and date the adverse event report when it is reviewed. For this protocol, only directly related SAEs/UPIRTSOs will be reported to the IRB.

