## 5.7.2 Stopping Rules

Any serious adverse event which is determined to reasonably be related to the study device by the sponsor-investigator will result in immediate discontinuation of the therapy. If 5 patients develop serious adverse events, the study will be halted with re-review required by the Mayo IRB prior to consideration of study resumption.

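### Safety is the sole primary objective, but AE differences rest on event totals with no per-man measure or named main safety population; separately, the last AE call can precede the end of the 5.2 follow-up period

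*Combined protocol and SAP*

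**What the plan says.** **Objective.** Section 2.1 lists one primary objective: "Evaluate the safety of the RestoreX® device when used 30 minutes once daily, twice daily, three times daily, and in an open label fashion". The protocol names no primary safety endpoint and no test for it.

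**Analysis of AEs.** Section 4.3.3 says: "Differences in AE's will be determined based on total number of reported events as well as individual assessments of each individual event". The same section lists chi-squared and Fisher's tests among the methods to be used where appropriate, without tying either to AEs.

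**Who is analysed.** The next paragraph of 4.3.3, on how well men can use the device, says: "Data will be analyzed both with and without these non-compliant / dropout men included". It gives three non-compliance criteria joined by 'and', two on technique and one on days of use: "failure to perform traction for at least 90% of days recommended". Neither version is named as the main one for safety. Under section 5.7.2, a serious AE determined to be "related to the study device by the sponsor-investigator will result in immediate discontinuation of the therapy".

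**Size.** Section 4.1.5: "A goal of 25 patients will be enrolled into each arm of the study, with an estimated 120 enrolled to achieve this number".

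**Timing.** Section 4.2 allows the 3-month visit to be up to 1.5 months late, starts a 3-month open-label phase after it, and sets a final AE call at 9 months; section 5.6 repeats the 9-month call. Section 5.2 ends follow-up at 9 months or at 3 months after last treatment, if that is later. Section 5.4 describes telephone review for up to 3 months after study completion.

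**The concern.** With safety as the sole primary objective, a reader will want to know what share of men had an AE on each schedule. An event total does not answer that: one man with several episodes and several men with one episode each give the same figure. The text does not say whether a complaint that recurs is one event or many.

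The population matters too. A man who leaves because of an AE is a dropout, so an analysis without dropouts selects on the outcome it is meant to measure. All three non-compliance criteria describe device use. Untreated controls can therefore leave the reduced set in the randomised phase only as dropouts, whereas device-arm men can leave by either route.

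Section 2.1 also names open-label safety separately, but the AE sentence in 4.3.3 does not separate the phases. Controls may use the device once the open-label phase starts, so pooling the phases would blur the comparison with no treatment.

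Finally, if the last scheduled AE contact comes before the defined follow-up period ends, late events in those men depend on less structured reporting.

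**Working it through.** **The plan's own figures.** No rate, sample size or power is given for safety. The enrolment figure reproduces: 25 × 4 = 100 retained from 120 enrolled, a loss of 20/120 = 16.7%, or about 5 of 30 men per arm. The stated effect size of 0.3370 concerns curvature and also reproduces (one-way ANOVA, 4 × 25, 80% power, two-sided 0.05: 0.33699). It does not bear on AEs.

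**1. Unit of analysis.** As an arithmetic illustration with an assumed total, take 10 events in an arm of 30. They fit anything from 1/30 = 3.3% to 10/30 = 33.3% of men affected. This shows that a total does not determine the share of men affected. It does not measure how far this trial's result would be off.

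**2. Who leaves the reduced set.**
- Dropouts leave in every reading.
- A man who stops therapy but stays in follow-up leaves only if failing one criterion is enough. On the days criterion with 91 recommended days (3 months), 10 missed days give 81/91 = 89.0%, below 90%. With 137 days (4.5 months), 14 missed days give 123/137 = 89.8%.
- If all three criteria must fail together, he is not clearly removed. Nor does 4.3.3 say whether days after a required stop still count as recommended.

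**3. Direction of bias.** Assume a 25% AE rate (the transient-pain figure that section 3.1 cites for an earlier device, not a planned rate here), so 30 × 0.25 = 7.5 men affected on average. Remove 5 of the 30, of whom k had the AE. The rate in the reduced set is (7.5 − k)/25:

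| k | 0 | 1 | 2 | 3 | 4 | 5 |
|---|---|---|---|---|---|---|
| rate | 30% | 26% | 22% | 18% | 14% | 10% |

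The all-men rate is 25%. The reduced set understates it only if at least 2 of the 5 had an AE; otherwise it overstates it.

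**4. Timing.** Let d be the lateness of the 3-month visit in months. With device use to the end of a full open-label phase, last use is at 3 + d + 3, and the 5.2 period ends at max(9, 3 + d + 3 + 3).

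| d | last use | 5.2 period ends | gap after 9-month call |
|---|---|---|---|
| 0 | 6.0 | 9.0 | 0 |
| 0.5 | 6.5 | 9.5 | 0.5 |
| 1.0 | 7.0 | 10.0 | 1.0 |
| 1.5 | 7.5 | 10.5 | 1.5 |

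The gap is also 0 if last use falls at or before month 6.

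**The case against.** Five objections deserve an answer.

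- **The AE sentence promises more than totals.** It adds an assessment of each event, and Fisher's and chi-squared tests normally compare counts of men. A per-man comparison by event type is therefore one plausible reading. This stands in part: the plan permits a per-man analysis but does not state one, and the measure it does state is the total. A reader might infer an inflated false-positive rate, but 4.3.3 assigns no test to the totals, so no such rate can be attached to the plan.
- **The with-and-without sentence may not concern AEs.** It sits in a paragraph on device use and never mentions them. This stands: applying it to AE data is a reading of unrestricted wording. A reader might infer that the plan removes harmed men and so makes the device look safer. The documents do not support that, because the all-men version is planned as well, removal of men still in follow-up depends on how the criteria combine, and the bias can go either way.
- **The phases can already be separated.** AEs are asked about at the 3- and 6-month visits (5.6) and dated on the AE form (5.7.1). True, so only the reporting rule is missing.
- **Nine months is the nominal schedule.** Section 4.2 invites self-report for 3 months after therapy ends, 5.4 follows unresolved AEs and describes telephone review after completion, and 5.6 records later serious AEs that are possibly related. These cover part of the gap, but 5.6 still fixes the call by calendar.
- **Counting all randomised men has a cost.** Device-arm men who never used the device dilute harm. This stands, and the fix allows for it.

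**Conclusion.** The point holds in a limited form and should be fixed. For its only primary objective, the plan states an event total where the number of men affected is the clearer measure and can be obtained from data already collected. It names no main population for safety. This does not mean that the safety analysis is biased as planned: the all-men version exists, and any effect of the reduced set depends on three unstated matters, namely whether the sentence covers AEs, how the criteria combine, and how many of the excluded men had an AE.

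The timing mismatch is real but conditional. It runs from 0 to 1.5 months and assumes a late first visit with device use continuing past month 6. It would be wrong to infer that follow-up is cut short for every man.

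The 10-event and 25% examples rest on assumed values and do not measure the defect.

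**What to change.** In section 4.3.3:

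- Make the main safety summary the number and percentage of all randomised men with at least one AE, overall and by event type, by arm for the randomised phase, with exact 95% confidence intervals and Fisher's test.
- State how many device-arm men never used the device.
- Give event counts per man as a secondary summary, and say how a recurring complaint is counted.
- Report open-label AEs separately, in line with 2.1.
- For safety, use the version without non-compliant and dropout men only as a sensitivity analysis, and list AEs that led to withdrawal.

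Reconcile 4.2, 5.2, 5.4 and 5.6 so that the last scheduled AE contact and the defined follow-up period agree.

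**Cost.** The analysis change is wording. Subject identifier, AE dates and impact on withdrawal are already on the AE form (5.7.1), and Fisher's test is already listed. The downsides are slightly more analysis work, less repeat-event detail in the headline figure (kept in the per-man counts), possible dilution from never-users and, depending on how the sections are reconciled, later calls for men with late visits.

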## 3.2 Preliminary Data

Currently, there is a small amount of preliminary data available on the RestoreX® instrument. During the developmental phase of the device, a quality improvement project was performed to evaluate the clamping portion (see **Attachment – Quality Improvement Summary**). It was felt that the clamp represented the most critical aspect of the device, as this was where the majority of discomfort occurred with other devices. Additionally, the clamp needed to provide sufficient friction to allow adequate traction without having the glans of the penis dislodge from the device.

A total of 15 patients participated in the quality improvement project and had the clamps applied under direct supervision for 30 minutes. After the 30 minutes, all patients reported 0/10 pain, and only minimal transient erythema was documented by the physician. The clamp was again applied, and traction forces were administered to determine if the clamp was able to remain intact despite stretching forces applied. This also resulted in a successful outcome, with all patients able to successfully achieve a minimum required tension of 1 kg, with a 36% safety factor achieved before any discomfort was reported among any patient. During the testing, patients reported improved comfort with the use of a wrap such as gauze or Coban, which permitted additional traction in all patients.

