#### 5 SAFETY AND ADVERSE EVENTS

#### 5. 1 Definition of Adverse Event

Unanticipated Problems Involving Risk to Subjects or Others (UPIRTSO) - any unanticipated problem or adverse event that meets the following three criteria:

Serious: Serious problems or events that results in significant harm, (which may be physical, psychological, financial, social, economic, or legal) or increased risk for the subject or others (including individuals who are not research subjects). These include: (1) death; (2) life threatening adverse experience; (3) hospitalization - inpatient, new, or prolonged; (4)

disability/incapacity - persistent or significant; (5) breach of confidentiality and (6) other problems, events, or new information (i.e. publications, interim findings, product labeling change) that in the opinion of the local investigator may adversely affect the rights, safety, or welfare of the subjects or others, or substantially compromise the research data, AND

Unanticipated: (i.e. unexpected) problems or events are those that are not already described as potential risks in the protocol, consent document, not listed in the Investigator's Brochure, or not part of an underlying disease. A problem or event is "unanticipated" when it was unforeseeable at the time of its occurrence. A problem or event is "unanticipated" when it occurs at an increased frequency or at an increased severity than expected, AND

Related: A problem or event is "related" if it is possibly related to the research procedures.

Adverse Event - an untoward or undesirable experience associated with the use of a medical product (i.e. drug, device, biologic) in a patient or research subject.

Serious Adverse Event - adverse events are classified as serious or non-serious. Serious problems/events can be well defined and include:

- Death
- Life threatening adverse experience
- Hospitalization
- Inpatient, new, or prolonged; disability/incapacity
- And/or per protocol may be problems/events that in the opinion of the sponsor-investigator may have adversely affected the rights, safety, or welfare of the subjects or others, or substantially compromised the research data.

All AEs that do not meet any of the criteria for serious, should be regarded as non-serious AEs.

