## 5.6 Recording of Adverse Events

The study team will seek information on adverse events by specific questioning between baseline and the 3 month and 6 month visits. At 9 months from the date of study initiation, the patient will be contacted via telephone for an additional assessment of any adverse events experienced. Information on all adverse events will be recorded immediately in the adverse event section of the specific questionnaire as well as in an adverse event form (see **Attachment – Adverse Event Form**).

All adverse events occurring during the study period will be recorded. The clinical course will be followed until resolution, stabilization, or until it has been ultimately determined that the study treatment or participation is not the probable cause. Serious adverse events that are still ongoing at the end of the study period will be followed up, to determine the final outcome. Any serious adverse event that occurs after the study period and is considered to be at least possibly related to the study treatment or study participation will be recorded and reported immediately.

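### For the primary safety objective, the only defined comparison of adverse events between schedules is a total count; no use of the recorded intensity is specified

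*Combined protocol and SAP*

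**What the plan says.** Section 2.1 has a single primary objective: "Evaluate the safety of the RestoreX® device when used 30 minutes once daily, twice daily, three times daily, and in an open label fashion". Section 4.3.3 gives one sentence on how AEs will be compared: "Differences in AE's will be determined based on total number of reported events as well as individual assessments of each individual event". It does not explain the second limb, name a test for AEs specifically, or mention intensity.

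Section 5.7.1 lists intensity among the AE form fields, under "Information collected on the adverse event form (and entered into the research database". The sections differ on which events get a form:

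- Section 5.6 covers every event: "Information on all adverse events will be recorded immediately in the adverse event section of the specific questionnaire", and also in an AE form.
- Section 5.7 has the form completed once any AE is identified.
- Section 5.7.1 names serious events only: "An adverse event form will be completed for any serious adverse event".

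Section 5.1 divides events in two by seriousness: "All AEs that do not meet any of the criteria for serious, should be regarded as non-serious AEs". Increased severity is mentioned there only as part of the definition of an unanticipated problem. The text available gives no intensity scale. The AE form is an attachment that was not available, and it may contain one.

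**The concern.** The randomised arms differ in daily traction time: none, 30, 60 or 90 minutes. More time on the device could produce more complaints, or the same complaints in a worse form. A total count responds only to the first. A count by type of event has the same limit, because mild and severe pain both count as pain.

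The protocol's own background suggests that most events will be minor. After a 30-minute test of the clamp in 15 patients, section 3.2 reports that "all patients reported 0/10 pain, and only minimal transient erythema was documented by the physician". Section 3.1 cites transient pain in 25% and erythema in 2% with another device. A total made up mostly of minor events says little about whether a longer schedule causes worse ones, which is a central part of the primary question.

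**Working it through.** **The plan's own figures.** No figure is stated for the AE comparison. The power statement in section 4.3.2 concerns curvature: ANOVA, 4 arms of 25, 80% power, effect size 0.3370. It reproduces (0.33699 from the noncentral F with 3 and 96 degrees of freedom and noncentrality 100 × f²), but it does not bear on AEs.

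**Inputs.** From the plan: 25 men per arm (4.3.2) and two-sided 0.05 (4.3.3). Assumed, because the documents give no AE rates for this device by schedule: an average of one event per man in the reference arm, and a moderate-or-worse AE in 4% of men there (1 of 25).

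**Step 1: total count.** Take total events per arm as Poisson and compare two arms with the exact conditional test: given m events in all, the number in one arm is Binomial(m, 0.5) under no difference. The mean total is 25 × events per man.

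| Mean events, arm A v arm B | Trials in which the count test rejects |
|---|---|
| 25 v 25 (intensity shifts, number does not) | 3.7% |
| 25 v 31 (25 × 1.24; worse events are additional) | 10.1% |
| 25 v 33 (25 × 1.32; worse events are additional) | 15.1% |

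The first row follows by construction: with equal expected counts the test rejects only at its own size. It shows what a count cannot measure; it does not predict what will happen in this trial.

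**Step 2: men with a moderate-or-worse AE.** Exact power of Fisher's test is the sum of Binomial(25, p1) × Binomial(25, p2) probabilities over all tables with p < 0.05.

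| Moderate-or-worse AE, arm A v arm B | Expected men | Unadjusted power |
|---|---|---|
| 4% v 12% | 1 v 3 | 3.5% |
| 4% v 16% | 1 v 4 | 10.9% |
| 4% v 20% | 1 v 5 | 23.0% |
| 8% v 24% | 2 v 6 | 21.8% |
| 4% v 28% | 1 v 7 | 53.4% |
| 4% v 36% | 1 v 9 | 78.1% |

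**Step 3: multiplicity.** Four arms give 4 × 3 / 2 = 6 pairs. At 0.05 / 6 = 0.0083 the last two rows fall to 20.7% and 47.1%. It therefore matters which pairs are named in advance.

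**Reading.** The intensity comparison can show a shift that the count cannot, but at 25 per arm it becomes a reasonably powered test only when the shift is seven- to nine-fold from 4%. For three- to five-fold shifts it misses the difference in at least 77% of trials (100 − 23.0).

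**The case against.** A reader might infer that the plan ignores intensity and that a harsher schedule would simply look as safe as a gentler one. The documents do not support that, for four reasons.

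1. The sentence in 4.3.3 does not stop at counts. An assessment of each event could draw on everything on the form, including intensity, outcome, action taken and effect on withdrawal. This stands: the accurate statement is that no use of intensity is specified. But an undefined review fixes no comparison in advance. A rule fixed beforehand is worth having here, since section 6.1 records that the study is led by the device's inventor.
2. Other channels exist. Questionnaire pain is compared among groups (2.2, objective 3), serious events feed the stopping rule (5.7.2), and dropout and non-compliance are analysed (4.3.3). These might pick up part of a shift. They do not replace an intensity comparison: pain is a secondary outcome and only one complaint, the five-patient rule counts across the whole study rather than by schedule, and under 5.1 a severe event can still be non-serious.
3. It is not certain that intensity is recorded for every event. Sections 5.6 and 5.7 say so, but 5.7.1 ties the form to serious events. If the narrower reading applied, the data for mild and moderate events would be missing. This stands, and the fix must cover it.
4. The favourable power figures rest on assumed rates and a large shift. This also stands; the smaller shifts above show how quickly power falls.

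**Conclusion.** The point holds as a gap in the analysis of the primary objective. The one defined between-arm AE measure is a total, which cannot register a change in intensity at equal numbers, and no use is specified for the intensity field. How much this matters depends on rates that the documents do not give. On the assumed rates, unadjusted power of the added comparison ranges from about 4-23% (4% v 12-20%) to about 53-78% (4% v 28-36%), with 25 men per arm and before any multiplicity correction. The added analysis should be read mainly as estimation: a by-arm picture of how bad the events were, with intervals. It is worth doing because it is cheap and bears directly on the primary question. It would not make the trial well powered for safety.

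**What to change.** In section 4.3.3, for the randomised 0-3 month period:

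- State the intensity scale, or refer to the one on the AE form if it has one.
- Classify each man by his worst recorded AE intensity: none, mild, moderate or severe.
- Report by arm the proportion with at least one moderate-or-worse AE, with 95% confidence intervals, and compare by Fisher's exact test. Name in advance which arms are compared.
- Report the worst-intensity distribution by arm and compare it by Wilcoxon test.
- Present these alongside the total counts, and say what the assessment of individual events consists of.

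Tabulate the open-label period in the same way, descriptively, since section 2.1 includes it in the objective. Reconcile sections 5.6 and 5.7 with 5.7.1 so that intensity is recorded for every AE, not only serious ones.

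The cost is a few sentences in the plan and one table, using tests that 4.3.3 already lists. The downside is one or two more safety comparisons. If the form is in practice completed only for serious events, there is also the work of extending it to all events.
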